2.1.2. Secondary Objectives

- To evaluate change in other skin biomarkers of atopic dermatitis in target lesions treated with crisaborole ointment 2% or vehicle.*
- To evaluate normalization of biomarker and gene expression levels in lesional skin treated with crisaborole ointment 2% or vehicle.*
- To evaluate changes in AD clinical sign and symptom severity in target lesions treated with crisaborole ointment 2% or vehicle.*
- To assess the safety and local tolerability of crisaborole ointment 2% in subjects with mild to moderate AD.*

CCI

- CCI [REDACTED]

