3.2. Secondary Endpoint(s)

- *Change from baseline in other skin biomarkers in target lesions treated with crisaborole ointment 2% or vehicle at Day 15.*
- *Biomarker and gene expression level in lesional skin treated with crisaborole ointment 2% or vehicle at Day 15 and levels in non-lesional skin at Baseline.*
- *Change from baseline in lesion severity as measured by TSS, ISGA, and Pruritus Numerical Rating Scale at each visit up to Day 15.*
- *The incidence of treatment emergent AEs and SAEs.*

CCI [REDACTED]

- █ [REDACTED]
- █ [REDACTED]
- █ [REDACTED]
- █ [REDACTED]
- █ [REDACTED]
- █ [REDACTED]

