5.2.3. Analyses for Biomarkers

The skin biopsy samples will be analyzed using immunohistochemistry (IHC), gene arrays and gene expression of specific genes to elucidate the mechanism of action of Crisaborole, which will be done using Taqman Low Density Array (TLDA) PCR for 48 genes including housekeeping genes as well as single gene PCR for few genes that are below detection level on TLDA. TLDA PCR expression values are estimated by $-\Delta Ct$ that is computed relative to RPLPO housekeeping gene. Measurements under the limit of detections are imputed as 20% of the minimum value observed for that gene.

The gene expression data is modeled using a mixed effect model with Time, Tissue, and Treatment as a fixed effect and a random intercept for each patient. This formulation intrinsically models the patient correlation structure as in the case of a paired t-test, having the advantage that estimation of the main effects is possible even in the presence of missing values. This allows to use all available data at each time point rather than using only complete observations. This approach introduces less bias than restricting the analysis for those patients who completed the study. Contrasts are used to estimate the fold changes with treatment within each treatment group and conduct hypothesis testing. Changes with treatment will be estimated and per gene improvement will be defined as $-100 * (XW_{12,LS} - XW_{0,LS}) / (XW_{0,LS} - XW_{0,NL})$, $XW_{12,LS} - XW_{0,LS}$ represents the least square means for the treatment change and $XW_{0,LS} - XW_{0,NL}$ represents the least square means for the baseline differences.

The microarray data is processed using standard QC metrics and R packages. Expression measures are obtained using GCRMA algorithm. Adjustments by batch effect and clinical variables are carried out using ComBat. Probe-sets with at least 15 samples with expression

values larger than 3 are kept for further analysis. Expression values are modeled using mixed-effect models with fixed factors Time, Tissue and Treatment and a random effect for each patient. Fold changes for the comparisons of interest are estimated and hypothesis testing was conducted on such comparisons using contrasts under the general framework for linear models. P-values from the moderated (paired) t-test were adjusted for multiple hypotheses using the Benjamini–Hochberg procedure which controls the False Discovery Rate (FDR).

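### The per-gene improvement percentage shares its lesional baseline between numerator and denominator and has no baseline-difference condition or interval, so it is unstable and shifted upward for genes with little lesional versus non-lesional difference

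*SAP*

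**What the plan says.** SAP 2.1.2 lists a secondary objective: "To evaluate normalization of biomarker and gene expression levels in lesional skin treated with crisaborole ointment 2% or vehicle". The matching endpoint in SAP 3.2 is "Biomarker and gene expression level in lesional skin treated with crisaborole ointment 2% or vehicle at Day 15 and levels in non-lesional skin at Baseline".

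SAP 5.2.3 models the gene expression data with a "mixed effect model with Time, Tissue, and Treatment as a fixed effect and a random intercept for each patient". It then states: "Contrasts are used to estimate the fold changes with treatment within each treatment group and conduct hypothesis testing". Next comes the index: "Changes with treatment will be estimated and per gene improvement will be defined as" a ratio with a leading minus sign, "100 * (XW_{12,LS} - XW_{0,LS}) / (XW_{0,LS} - XW_{0,NL" (closing brackets omitted here). The denominator "represents the least square means for the baseline differences". I read the first term as the post-treatment (Day 15) lesional value; its week label is a separate matter.

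Three things are absent from the definition:
- any requirement that the gene differ between lesional and non-lesional skin at baseline;
- any confidence interval for the ratio;
- any statement of what the index shows when nothing has happened.

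The only gene filter in the section, "Probe-sets with at least 15 samples with expression" above a set level, belongs to the microarray paragraph. It screens on expression level, not on disease difference.

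**The concern.** The baseline lesional mean enters the numerator with a minus sign and the denominator with a plus sign. If it is high by chance, the lesion appears to fall after treatment and also appears further from non-lesional skin at baseline. After the leading minus sign, both errors push the index toward a positive percentage. When the true baseline difference is small, the denominator is mostly noise and can change sign, so the ratio can be very large in either direction.

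The TLDA list in Protocol Section 3 (Skin biopsy and biomarkers) has 46 named targets, including PDE4A, PDE4B, PDE4D, IL-2 and IL-9. The documents give no baseline lesional versus non-lesional difference for any of them. In a mechanism study, a positive within-arm percentage for such a gene could be taken as normalization by the drug when it is shared-baseline noise.

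**Working it through.** **Inputs.** n = 30 and a maximal SD of 3 for the log2 change (Protocol 9.1). One biopsy per target area on Day 1 and Day 15, and one non-lesional biopsy on Day 1 (Protocol Section 3). Random patient intercept (SAP 5.2.3), so residuals of different biopsies are independent with one common variance. Two assumptions are mine: a separate mean for each tissue, time and treatment cell, and an SD of 3 for the lesional minus non-lesional difference as well.

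**The plan's own figure.** The half width of the 95% CI for the change is 1.96 × 3/√30 = 1.07, which agrees with the stated value below 1.1 (1.12 with the t quantile). The documents state no figure for the index itself.

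**Null median.** Let a, b and c be the errors in the Day 15 lesional, baseline lesional and baseline non-lesional means. With no drug effect and D = 0:

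index = 100 × (b − a)/(b − c)

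This is a ratio of correlated zero-mean normals, hence Cauchy, with median 100 × Cov(b − a, b − c)/Var(b − c). With independent errors of variance v this is 100 × v/(2v) = 50%. The correlation is 0.5, so the Cauchy scale is 100 × √(1 − 0.25) = 86.6. It follows that:
- the quartiles are 50 ± 86.6, or about −37% and 137%;
- the central 95% is 50 ± 86.6 × tan(0.475π), or about −1050% to 1150%;
- about 67% of null results are positive, and about 27% exceed 200% in absolute value.

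n and SD cancel, so none of this depends on them. Simulation with 400,000 draws agreed. So did 1,500 fitted random-intercept models with 15% of Day 15 biopsies missing, with medians of 49% and 52% in the two arms. If numerator and denominator used independent baselines, the null median would be 0%.

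**Other error structures, D = 0.**

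| Assumption | Null median |
|---|---|
| Independent, equal variance, arm-specific baseline | 50% |
| Day 1 baseline pooled over both lesions: 0.5v/1.5v | 33% |
| Share ρ of within-patient variance common to a lesion over time, 50 × (1 − ρ), ρ = 0.3, 0.5, 0.7 | 35%, 25%, 15% |
| Non-lesional variance k times lesional, 100/(1 + k), k = 0.5, 2 | 67%, 33% |

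**Non-zero D, no drug effect (n = 30, SD 3).**

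| D (log2) | 0 | 0.25 | 0.5 | 1 | 1.5 | 2 |
|---|---|---|---|---|---|---|
| Median | 50% | 40% | 23% | 4% | 0.2% | about 0% |

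The standard error of the denominator is 3/√30 = 0.548. At D = 0.5 the chance of a wrong sign is Φ(−0.5/0.548) = Φ(−0.91) = 18%. With SD 1.5 it is Φ(−1.83) = 3%. If the true improvement is 50%, the central 95% at SD 3 is about −180% to 280% for D = 1 and 26% to 74% for D = 4. For D = 1 at SD 1.5 it is about −5% to 105%.

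**Effect of a baseline cut-off.** I filtered on an observed baseline difference with unadjusted p < 0.05, with no drug effect and SD 3. By construction about 5% of null genes pass, and Benjamini-Hochberg adjustment cannot let more through. Among genes that pass, however, the median is still 50% at D = 0. It rises from 23% to 32% at D = 0.5 and from 4% to 16% at D = 1, because the filter favours genes whose lesional baseline was high by chance.

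**The case against.** The strongest reply is that this is a descriptive index with no inferential role. SAP 6.1.2.1 decides on adjusted p-values, and its reporting list does not include the percentage. The visible part of SAP Section 6 names no improvement output, though 6.3 is blacked out. The secondary endpoint names expression levels, not this ratio. All of that stands, and it limits the point to a secondary, descriptive result.

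The panel was also chosen for association with atopic dermatitis, so D = 0 may be uncommon, and SD 3 is the plan's maximum. Both are fair. Neither shows that every listed gene differs in lesions, and the null median does not depend on SD.

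It can also be said that values near ±1000% are visibly unstable and would mislead nobody. That is true of the extremes, but half of null results fall between about −37% and 137%, where a single percentage looks plausible.

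A reader might infer more than the documents support:
- **That the flaw favours crisaborole over vehicle.** It does not: the null median is the same in both arms, so the contrast between them is noisier but not shifted.
- **That it extends to every array probe-set.** The formula is in the PCR paragraph, and the microarray paragraph does not mention it.
- **That null genes will show 50%.** That figure needs independent, equal-variance errors and an arm-specific baseline. The SAP's baseline term carries no treatment label, and a pooled baseline gives 33%.

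**Conclusion.** The point holds for PCR-panel genes with a small baseline lesional versus non-lesional difference. For these the index has no stable value and leans upward. The null median is 50% under the SAP's random-intercept model with an arm-specific baseline, 33% with a pooled baseline, and about 15% to 67% across the other structures examined, always above zero. At n = 30 and SD 3 the sign is wrong in 18% of cases at D = 0.5.

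The median shift is negligible once D reaches about 1.5 log2 at SD 3. Because it depends on D/SD at a given n, that becomes about 0.75 at SD 1.5. The key biomarkers are little affected if they are clearly raised in lesions, but the documents give no baseline differences to confirm this. The adjusted tests, the crisaborole versus vehicle comparison and the primary decision rule are not biased by it. This is a reporting weakness in the secondary normalization objective that should be corrected before analysis, not a threat to the primary conclusions.

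**What to change.** In SAP 5.2.3:

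1. For all genes, make the Day 15 lesional minus baseline non-lesional contrast from the same mixed model, with 95% CI and by treatment, the main normalization result. It uses the two quantities named in the secondary endpoint, needs no division and leaves out the shared lesional baseline. Show the baseline lesional minus non-lesional difference beside it, so that a gene that never differed is not read as normalized.
2. Keep the improvement percentage as a supportive descriptive figure only. Limit it to genes whose baseline difference passes a stated cut-off (for example Benjamini-Hochberg adjusted p < 0.05), always with a Fieller or subject-level bootstrap 95% CI and the vehicle value alongside. State whether the baseline lesional mean is arm-specific or pooled.
3. State that the cut-off reduces how many null genes appear but does not remove the upward shift among weak-signal genes that pass, so a within-arm percentage is not by itself evidence of drug effect.

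The cost is SAP wording and a few lines of code on contrasts already estimated. The downside is that fewer genes will carry a percentage.

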### Skin biopsy and biomarkers

For all subjects, one 4.5 mm skin biopsy will be collected from each target treatment area on Day 1, and Day 15. In addition, on Day 8, subjects will be offered one optional 4.5 mm skin biopsy collected from each target treatment area, to provide additional samples for analysis. The biopsies on Day 8 and Day 15 will be collected in the vicinity, but at least 1 cm distant from where the biopsies were collected at Day 1, even if the target treatment area has cleared. One additional 4.5 mm biopsy will be collected from nonlesional skin on Day 1. Each biopsy will be cut in half. One half will be used to perform reverse transcriptase (RT) PCR and gene arrays and the other half will be used for immunohistochemistry analysis and hematoxylin and eosin (H&E) staining.

Parameters studied using IHC will include epidermal thickness (performed on H&E sections), Ki-67+ cells, Keratin 16 (K16), CD3+ T-cells, CD11C+ dendritic cells (DCs), Fc Epsilon+ dendritic cells (DCs), langerin+ cells (for langerhans cells), filaggrin.

Gene expression by RT PCR panel (skin ribonucleic acid [RNA]) will include levels of the following established cytokines associated with AD: IL-13, IL-19, IL-22, IL-17A, IL-23 (p19), IL-12/23 p40.

Gene expression by TLDA RT PCR will include the levels of the following established cytokines associated with AD: IL-1B, IL-2, IL-2RA, IL-5, IL-6, IL-8, IL-9, IL-10, IL-12p35, IL-12/23p40, IL-13, IL-15, IL-15RA, IL-17A, IL-17F, IL-19, IL-22, IL-23 (p19), IL-31, IL-32, K16, PDE4A, PDE4B, PDE4D, filaggrin, loricrin, periplakin, S100A7, S100A9, S100A12, MMP12, IFN-gamma, CXCL1, CXCL2, CXCL9, CXCL10, CCL20, elafin/PI3, hBD2, CCL13, CCL17, CCL18, CCL22, CCL26, FOXP3 and TSLP receptor, of which the following are considered the key biomarkers associated with AD pathways:

**S100A12** (general inflammation); **Keratin 16** (epidermal hyperplasia; proliferation marker (barrier function)); **Elafin/PI3** (Th17); **CCL17** (Th2); **CCL18** (Th2); **CCL22** (Th2); **IL13** (Th2). PDE4 expression will be quantified in the tissue by TLDA.

Gene arrays using Affymetrix UPlus 2 arrays will also be performed to allow for more global analyses of genomic changes and normalization of lesional samples towards non-lesional samples with treatment.

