### **9.3. Analysis of Biomarker Endpoints**

In addition to the key biomarkers, the other biomarkers endpoints in this study include (but may not be limited to) the following:

Parameters studied using immunohistochemistry (IHC) will include epidermal thickness (H&E staining), Ki-67+ cells, CD3+ T-cells, CD11c+ dendritic cells (DCs), FcEpsilonRI+ DCs, langerin+ cells, and FLG+ (filaggrin) cells. Gene expression endpoints from RT PCR or Gene array will include MMP12, IL-1B, IL-2, IL-2RA, IL-5, IL-6, IL-8, IL-9, IL-10,

IL-12p35, IL-15, IL-15RA, IL-17A, IL-17F, IL-19, IL-22, IL-31, IL-32, IL-23p19, IL-12/23p40, INF- $\gamma$ , CXCL1, CXCL2, CXCL9, CXCL10, CCL13, CCL20, CCL26, S100A7, S100A9, hBD2 (human  $\beta$  Defensive 2), FLG (filaggrin), LOR (loricrin), periplakin, FOXP3, and thymic stromal lymphopoietin (TSLP) receptor. PDE4A, PDE4B, and PDE4D expression will also be quantified.

The population for the analysis of the biomarkers will be ‘per protocol’ (PP) population, which includes any subject receiving  $\geq 1$  dose of investigational product, with both Day 1 and Day 15 biopsies done, and without protocol violations that were thought to impact the biomarker expression during the vehicle controlled period. All protocol deviations will be reviewed and assessed by the study team prior to database release. In general, all data will be summarized using descriptive statistics. No imputation will be made for missing data.

Comparison of pre- and post- treatment of skin treated with crisaborole ointment 2% or vehicle will be performed. Expression levels from RT PCR will be normalized to the housekeeping gene hARP (validated in other studies) and log2-transformed prior to analysis (reporting unit: Expression/hARP). Microarray data will be preprocessed using standard pipeline and log2 transformed expressions. Adjustments by batch effect and clinical variables will be carried out using ComBat, if needed. Mixed effect model will be used and p-values will be adjusted by Benjamini-Hochberg procedure.

Additionally, extensive bioinformatics tools will be employed to gain insights into the mechanism of action of crisaborole.

Correlation analysis will be performed to assess if change from baseline in biomarkers correlates with change in the lesion TSS.

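### The microarray model has no batch term after ComBat, so Day 1 to Day 15 array contrasts are distorted if the two visits fall unevenly across batches

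*SAP*

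**What the plan says.** SAP 5.2.3 sets out the array analysis in two steps. After GCRMA, "Adjustments by batch effect and clinical variables are carried out using ComBat". Then "Expression values are modeled using mixed-effect models with fixed factors Time, Tissue and Treatment and a random effect for each patient". Fold changes for comparisons that are not listed are tested by moderated (paired) t-tests, with Benjamini–Hochberg control of the false discovery rate. Batch is not in the model, and the covariates passed to ComBat are not named.

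Protocol 9.3 made the step conditional: "Adjustments by batch effect and clinical variables will be carried out using ComBat, if needed".

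Protocol Section 3 says the arrays are meant "to allow for more global analyses of genomic changes and normalization of lesional samples towards non-lesional samples with treatment". The same section provides that "one 4.5 mm skin biopsy will be collected from each target treatment area on Day 1, and Day 15", while non-lesional skin is biopsied on Day 1 only. For the gene expression model, SAP 5.2.3 adds that "Contrasts are used to estimate the fold changes with treatment within each treatment group and conduct hypothesis testing". A secondary endpoint (SAP 3.2) sets Day 15 lesional expression beside baseline non-lesional expression.

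Neither document says how many array batches there will be or how samples are allocated to them.

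**The concern.** ComBat estimates the batch effects from the same samples that are then tested. A later model without batch treats that correction as known and exact.

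Pairing within subject removes batch only when both members of the pair were run in the same batch. The contrasts most relevant to the stated purpose of the arrays cross visits: Day 15 against Day 1 in one lesion, and Day 15 lesional against Day 1 non-lesional skin. If Day 1 arrays were mostly run in one batch and Day 15 arrays in another, batch and visit are partly confounded in exactly these contrasts.

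The Benjamini–Hochberg procedure holds its stated rate only if the p-values given to it are valid, and the fold changes describe mechanism only if they are unbiased. At stake are the array results on mechanism and normalisation, in a trial set up to characterise mechanism.

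**Working it through.** Neither document states an error rate, a power or a batch layout for the arrays, so there is no figure of the plan's own to reproduce.

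**Inputs from the documents.** About 30 subjects with a Day 15 biopsy (Protocol 9.1). Five arrays each: two lesions and one non-lesional site on Day 1, and two lesions on Day 15 (Protocol Section 3; the optional Day 8 biopsy is left out).

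**Assumptions.** Nominal two-sided level 0.05. Two batches. A subject's samples from one visit share a batch. A share p of Day 1 samples is in one batch and the same share p of Day 15 samples in the other, with p from 0.5 (balanced) to 0.9. Residual SD 1, patient SD 0.7, batch SD 1. Ordinary t-tests stand in for the moderated ones.

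**Step 1: closed form.** With two equal batches, the correlation between visit and batch is 2p − 1. Let k = 1 − (2p − 1)² = 4p(1 − p), the part of the visit information that is free of batch.

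- ComBat preserves the design factors: the estimate is about right, but the standard error is too small by a factor √k. True type I error ≈ 2[1 − Φ(1.96√k)].
- ComBat does not preserve them: part of the real change is removed as batch. About k of it is kept if both lesions change. About 1 − (2p − 1)²/2 is kept if only one of the two lesions changes.

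| p | k | Type I error, preserved | Kept, both lesions change | Kept, one lesion changes |
|---|---|---|---|---|
| 0.5 | 1.00 | 0.050 | 1.00 | 1.00 |
| 0.7 | 0.84 | 0.072 | 0.84 | 0.92 |
| 0.8 | 0.64 | 0.117 | 0.64 | 0.82 |
| 0.9 | 0.36 | 0.240 | 0.36 | 0.68 |

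**Step 2: simulation of parametric ComBat, within-treatment change.**

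| p | Type I, preserved | Type I, not preserved | True change of 1.00 estimated as, not preserved |
|---|---|---|---|
| 0.5 | 0.053 | 0.049 | – |
| 0.7 | 0.073 | 0.051 | 0.84 to 0.91 |
| 0.8 | 0.114 | 0.048 | 0.67 to 0.80 |
| 0.9 | 0.219 | 0.036 | 0.38 to 0.66 |

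The lower estimate in each range is for a change in both lesions. The losses are therefore 9–16%, 20–33% and 34–62%. With the design factors preserved, Day 15 lesional against Day 1 non-lesional skin behaves almost the same: 0.051, 0.072, 0.112 and 0.223. With batch in the model on uncorrected data, type I error stayed between 0.047 and 0.054 in every set-up.

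**Step 3: false discovery rate and power** (nominal 0.05; 20% of genes changed by one residual SD in both lesions).

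| p | FDR, preserved | FDR, batch in model | Power, preserved | Power, not preserved | Power, batch in model |
|---|---|---|---|---|---|
| 0.6 | 0.047 | 0.040 | 0.88 | 0.85 | 0.87 |
| 0.7 | 0.069 | 0.041 | 0.87 | 0.69 | 0.82 |
| 0.8 | 0.145 | 0.039 | 0.85 | 0.36 | 0.67 |
| 0.9 | 0.420 | 0.032 | 0.79 | 0.03 | 0.25 |

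**Step 4: sensitivity.** At p = 0.8 with factors preserved, type I error is 0.084 to 0.155 for patient SD 0.3 to 1.2, and 0.123 with four batches. A separate simulation with patient SD 1, batch SD 0.5 and paired t-tests gave 10% at p = 0.75 and 28% at p = 0.9. With factors not preserved, the one raised value was 0.069 (p = 0.8, patient SD 1.2).

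**Step 5: what is untouched.** The crisaborole–vehicle difference in change stays at 4.7–5.2% when a visit's samples share a batch. If all of a subject's samples share a batch, every method and contrast gives 0.049–0.053.

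**The case against.** The strongest reply is that the uneven layout is the reviewer's condition. Protocol 7.2 leaves sampling and handling to a separate manual, and a careful laboratory may keep each subject together. That stands: with balanced batches the plan as written is adequate, and the largest distortions need about 90% separation by visit.

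Several stronger readings do not hold:

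- A reader might infer that array p-values will be too small. That follows only if ComBat preserves Time, Tissue and Treatment. The mention of clinical variables makes this plausible, but it could equally mean variables to be removed, and then the error is mainly shrinkage.
- A reader might infer that genes would be called normalised too often. SAP 5.2.3 defines improvement as a ratio of least-square means with no test attached. A p-value that is too small for Day 15 lesional against non-lesional skin would argue against normalisation.
- A reader might extend the problem to the primary biomarkers. The seven key genes are in the PCR panel, for which no ComBat step is described, and their stated hypothesis compares crisaborole with vehicle.
- Making ComBat a fixed step is not in itself a fault. Both documents let the SAP modify the protocol, and a fixed step removes discretion.

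The SAP also does not list the array comparisons. That cross-visit contrasts are among them is an inference from the stated use, "more global analyses of genomic changes and normalization of lesional samples towards non-lesional samples with treatment", and from the within-group contrasts described for gene expression.

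**Conclusion.** The point holds conditionally. Under uneven batches, the planned two-step analysis distorts cross-visit array contrasts whichever way ComBat is set up: false positives of about 7%, 11% and 22% at 70%, 80% and 90% imbalance, or estimated changes reduced by about 9–16%, 20–33% and 34–62%. The SAP does not settle which applies. The sizes rest on an assumed layout, assumed variances and ordinary t-tests. The effect is negligible if visits are balanced over batches or each subject's samples share a batch. It reaches only the array results on mechanism and normalisation, so the priority is minor to moderate.

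**What to change.** In SAP 5.2.3, run the array tests on the GCRMA values before ComBat, with batch as a fixed factor in both the mixed model and the linear model behind the moderated t-test. Use ComBat-adjusted values only for plots and clustering. Naming ComBat's covariates alone would not be enough, since it would only show which of the two errors applies. Where arrays have not yet been run, process all of a subject's samples in one batch, so that batch cancels within subject.

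The cost is a sentence and a model term: one degree of freedom per extra batch. If batch and visit largely coincide, cross-visit intervals widen and power falls, to 0.25 at 90% imbalance in the example above. That loss reflects real confounding; the higher power of preserved ComBat there (0.79) comes with a false discovery rate of 0.42. This is a cheap improvement.
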